Evidence-based lifestyle weight loss interventions have been implemented and demonstrated favorable results in clinical settings targeting populations with various diseases (e.g., cancer, type II diabetes, hypertension) (71-82). These programs focused on and utilized resources in urban areas. To utilize the same intervention strategies from these programs may not be feasible and effective for rural populations to lose weight due to their unique personal (e.g., family roles, living priorities) and environmental (e.g., limited resources) factors (83-85). Barriers to healthy diet and the lack of recreation facilities explain variations in health behaviors in rural populations. These populations also have lower self-efficacy in healthy diet and exercise (i.e., belief of the ability to eat healthy/exercise when there are barriers), and minimal social support from family and friends to promote healthy lifestyle (83-85). Individuals with lower self-efficacy and social support are less likely to overcome barriers to achieve improvement in health behaviors (86). Self-efficacy and social support are critical in successful weight loss efforts by supporting the expectation, setting goals, establishing healthy dietary habits, increasing daily physical activity, and persistence in overcoming barriers (87, 88). However, tailored strategies to improve self-efficacy and social support for rural populations are understudied. Moreover, although remotely accessible interventions are suggested to achieve more weight loss with better cost-effectiveness than face-to-face interventions in rural areas (89, 90), web-based interventions have not provided clinically meaningful weight loss (91). Therefore, the proposed study, HERO, will include a telephone-based weight loss intervention, specifically focused on improving self-efficacy and increasing social support to help rural populations overcome barriers,

improve healthy diet and physical activity, and maintain a healthy weight, with the goal of reducing obesity-related cancer risk and health disparities.

B.1.e A Point-of-care Approach to Assess Body Composition and Cancer Risk in Rural Populations

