The objective of the behavioral component is to promote increased self-efficacy and social support for lifestyle modifications and gradually facilitate participants' transition toward successful independent self-regulation of a healthy diet and physical activity. The behavioral component focuses upon the acquisition and practice of self-regulatory skills in conjunction with a continuous problem-solving model of behavior change to empower participants to exert greater control over their behavior, cognition, and environment. The behavioral component is designed to: a) increase health knowledge of the benefits of physical activity and dietary modifications; b) enhance self-efficacy and positive outcome expectancies through the promotion of a series of successful experiences in changing exercise and eating behavior; and c) improving self-regulation of exercise and eating behaviors through the use of goal-setting, self-monitoring, stimulus control, cognitive restructuring, and barrier problem-solving strategies. The efficacy of this approach for promoting adoption and maintenance of exercise and dietary behavior change has been demonstrated in prior randomized controlled trials that [name] has served as principal and co-investigator on other studies (106-109).

C.5 Active Control Group

At the beginning of the study, participants randomized to the active control arm will receive education brochures (will be submitted in the first amendment) describing the American Institute for Cancer Research physical activity and dietary guidelines. Participants will be asked to meet the 2018 Physical Activity Guidelines for Americans (150 min/week of moderate-intensity exercise or 75 min/week of vigorous exercise), and increase fruit and vegetable intake, reduce fat intake, reduce sugary drink, increase consumption of whole grain, and increase water intake. An exercise manual with access Online YouTube videos (as another option) will be available as examples for proper exercise form for strength training. We will also encourage them to self-monitor weight, dietary intake, and physical activity through MyFitnessPal or paper log. To achieve the retention and provide motivation and strategies for behavioral change in the active control group, participants will receive a Fitbit and the lifestyle modification manual at the end of the study.

C.6 Covid-19 Safety Protocols and Planning

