Outcome assessments will be obtained at baseline and 15 weeks later at in-person visits by research staff blinded to treatment group assignment. All outcome assessments will be conducted at a community center or public location convenient to the participant. Each outcome measure will be collected through paper or online survey (through REDCap) and stored in REDCap (Research Electronic Data Capture).

C.7.a Primary Outcome: feasibility and acceptability

Completion rate and participation of the weekly telephone counseling session will be measured to evaluate the feasibility and acceptability of the 15-week telephone-based weight loss intervention.

C.7.b Secondary Outcome Assessment

Self-reported questionnaires and objective measures by research staff will be used (**Table 3**).

Table 3. Assessment Approach

Assessment	Approach	Time
Weight, height	Research staff using weight scale	2 mins
Body composition	Research staff using Styku 3D body scanner	10 mins
Hydration status	Research staff using urine specific gravity	3 mins
Lipid: Total cholesterol (TC), triglycerides (TG), high-density lipoprotein cholesterol (HDL-C), and low-density lipoprotein cholesterol (LDL-C)	Research staff (with training) using Cholestech LDX	3 mins
Inflammatory markers: C-reactive protein (CRP), Interleukin (IL)-6, TNF- α	Research staff (certified phlebotomists) conducting blood draw	5 mins
Objectively measured physical activity	Participants will wear ActivPAL for 7 days	--
IPAQ Leisure-Time Exercise Questionnaires	Self-reported via paper or online survey	5 mins
Diet diary (developed by NCI)	Self-reported via paper for 7 days	--
Healthy eating and weight SE questionnaires	Self-reported via paper or online survey	5 mins
Multi-dimensional Self-Efficacy scales	Self-reported via paper or online survey	5 mins
Social Support Inventory for Physical Activity	Self-reported via paper or online survey	5 mins
Social Support Inventory for Healthy eating	Self-reported via paper or online survey	5 mins
Physical Fitness	Research staff (with training) using standard protocols	15 mins

1. Anthropometric assessment

Body weight (kg) and height (cm) will be measured to calculate BMI (kg/m^2).

2. Body composition

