Objectively-determined minutes of PA participation will be assessed and The ActivPAL captures free-living sedentary and ambulatory PA and is well-established as one of the most accurate wearable activity monitors

(115). The monitor will be set to collect PA data using the manufacturer settings and is affixed to the midline of patients' right thigh in a waterproof pouch allowing for continuous wear time. Participants will be provided verbal and written instructions on how to wear the ActivPAL and wear the monitor 24 hours per day for the 7 consecutive days following the completion of the study assessment visits. In the event of wear time problems, patients must have at least 10 hours per day of wear time on 4 days of the week (including at least 1 weekend day) for a valid assessment. Monitors will be returned to trial staff via U.S. postal service.

Participants will also complete self-reported Leisure-Time Exercise Questionnaires (116) in the 1st and 15th week.

7. Dietary intake

All participants will complete 7-day food checklist for at the 1st and 15th week. This food checklist was developed by the National Cancer Institutes that comprised of a list of foods. Over the course of a day, participant makes a check beside a food each time she or he eats it. It yields estimates of macro nutrient intake, as well as intake by specific food groups. Participants in the weight loss intervention will also be encouraged to complete daily food log using MyFitnessPal (or paper log) during the trial. The food log and weekly summary of caloric and macronutrient intake will be regularly monitored by the trial's staff and registered dietitian to track adherence.

8. Self-Efficacy and Social Support

Participants will be asked to complete self-reported Healthy Weight and Eating Self-Efficacy, Multi-dimensional Self-Efficacy scales (117-119), as well as adapted Social Support Inventory for Physical Activity (SSPA) and Eating Habits (SSEH) questionnaires (120, 121).

9. Physical fitness

Participants will be asked to complete valid and reliable timed performance-related mobility tasks, such as 400-meter walk and lift and carry task (122-125). These assessments at baseline will serve as a reference to tailor exercise counseling for each participant.

C.9. Timeline

Table 4. Study Timeline

ACTIVITY	Year 1												Year 2											
	1	2	3	4	5	6	7	8	9	10	11	12	1	2	3	4	5	6	7	8	9	10	11	12
Database Development and Training	→																							

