We considered using a standard measure of body composition using Dual-energy X-ray absorptiometry (DXA) but opted not to as this is likely to add the burden of travel to facilities equipped with DXA. However, we will assess body composition using a 3-D Styku body scanner, which is portable to rural community-settings and can provide valid and reliable data on body composition. Together with using Cholestech LDX to evaluate participants' lipid profiles, the proposed study is innovative to test new point-of-care approaches to assess disease risk factors in rural populations.

D DATA HANDLING AND ANALYSES

D.1. Outcome Analysis Plan

D.1.a Primary outcome

The feasibility of completing the study is defined as the percentage of enrolled participants who complete the study. If we observe an 80% completion rate in the weight loss intervention group (n=30), the 85%, 90%, and 95% confidence intervals (CIs) for the completion rate would be (69.5, 90.5), (68.0, 92.0), and (65.7, 94.3), respectively. If the true completion rate is 80%, we have 95% power to rule out the unacceptable 50% completion rate with 95% confidence (one-sided).

The acceptability of the weight loss intervention is the percentage of participants in the weight loss intervention group who engage at least 75% of the weekly telephone counseling session. Intervention-related adverse events, satisfactory, and other feasibility assessments, such as the percent of initial contact to enrollment, reasons for consent refusal, barriers to adherence to weekly goals, and reasons for drop-out will also be assessed.

D.1.b Secondary outcome

Significance test for the preliminary efficacy of the lifestyle intervention will quantify the difference in means using repeated measures analysis of variance (ANCOVA) statistical model to adjust baseline values and control for the effect of age. The sample size of 30 participants in the weight loss group and at least 15 in the active control group is feasible to recruit for a pilot/preliminary efficacy study that accounts for a projected attrition rate of 20% yet also still provides adequate power to detect meaningful, moderate to large effect size (0.54-0.72) on weight loss, body composition, inflammatory markers, and lipid profiles.

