Analyses will be conducted using the intention to treat principle with last value carried forward approach used to account for data missing due to participant attrition. Exploratory analyses will compare outcomes including weight loss, changes in body composition, changes in physical activity and dietary intake, changes in lipid profiles and inflammatory biomarkers between the telephone-based weight loss group and the active control group. We will also examine whether social support and self-efficacy changes among participants from the weight loss group. These exploratory analyses will provide effect size estimates to inform the development of a large-scale phase II randomized controlled lifestyle weight loss intervention trial.

D.2. Data Management

As mentioned above, we will use REDCap as our data entry system. It will be used to store the baseline and follow-up questionnaires, will work directly with the OSU CCTS Research Informatics Services Core and will be

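### Self-efficacy and social support are to be analysed only as change within the weight-loss arm; no between-arm comparison is specified for them

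*Combined protocol and SAP*

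**What the plan says.** Section D.1.b (Secondary outcome) handles the non-primary outcomes in several steps.

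- It names a general model for preliminary efficacy, a "repeated measures analysis of variance (ANCOVA) statistical model to adjust baseline values and control for the effect of age", without listing in that sentence the outcomes it covers.
- It lists outcomes for comparison between the two arms: "Exploratory analyses will compare outcomes including weight loss, changes in body composition, changes in physical activity and dietary intake", followed by lipids and inflammatory markers.
- It then gives these two constructs a sentence of their own: "We will also examine whether social support and self-efficacy changes among participants from the weight loss group".
- It closes: "These exploratory analyses will provide effect size estimates to inform the development of a large-scale phase II randomized controlled lifestyle weight loss intervention trial".

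On the intervention, section B.1.d describes it as "specifically focused on improving self-efficacy and increasing social support to help rural populations overcome barriers", and C.4.d states: "The objective of the behavioral component is to promote increased self-efficacy and social support for lifestyle modifications".

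On data collection, Table 3 in C.7.b lists the self-efficacy and social support questionnaires among the secondary outcome assessments. Item 8 of C.7.b says "Participants will be asked to complete self-reported Healthy Weight and Eating Self-Efficacy, Multi-dimensional Self-Efficacy scales", together with the social support inventories. It does not restrict this to one arm. For timing, C.7 says "Outcome assessments will be obtained at baseline and 15 weeks later at in-person visits by research staff blinded to treatment group assignment".

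**The concern.** The trial has a randomized control arm, yet the only analysis sentence that names these scales does not use it. A before-after change in one arm combines any effect of the intervention with retest effects, possible regression to the mean, and whatever follows from simply being in a study. The controls are not inert: section C.5 gives them brochures, activity and diet goals, exercise videos and encouragement to self-monitor, so some movement among them is plausible.

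What is at stake is the estimate passed to the next trial. If the within-arm change is taken as the effect size for a two-arm design, it is off by the amount the controls shift: too large if they improve, too small if they decline. It would also be weak evidence that the behavioral component moved the constructs it was designed to move.

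**Working it through.** **Reading the text.** Outside D.1.b, no text on outcomes to be analysed names these scales. They are absent from Aim 2 (A.3), from the exploratory outcomes in C.1, and from the sentence in D.1.b that quotes detectable effect sizes of 0.54-0.72. Within D.1.b they appear once, in the one-arm sentence. The plan gives no figure for them, so there is nothing of its own to reproduce.

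**Were both arms measured?** Item 8 of C.7.b refers to participants generally. Item 7 (dietary intake), by contrast, says explicitly when a task, the daily food log, is for the weight-loss arm. Collection in both arms is therefore the natural reading, but it is an inference.

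**Inputs from D.1.b.** 30 in the weight-loss arm and at least 15 controls (up to 20 elsewhere in the protocol); projected attrition 20%. This gives 30 × 0.8 = 24 completers against 15 × 0.8 = 12 or 20 × 0.8 = 16.

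**Assumed inputs, not in the documents.** Two-sided 5% tests; a paired t-test within the arm; the same shift in both arms and no intervention effect; baseline to week-15 correlation r of 0.5-0.7; equal variances.

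**1. Chance that the within-arm test reports a change.** Noncentral t with n − 1 degrees of freedom and noncentrality δ√n, where δ is the shared shift in SDs of change. For example, with δ = 0.3 and n = 24, the noncentrality is 0.3 × √24 = 1.47 against a critical value of 2.07, giving 29%.

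| Shared shift (change SD) | n = 24 | n = 30 |
|---|---|---|
| 0.3 | 29% | 36% |
| 0.4 | 47% | 56% |
| 0.5 | 65% | 75% |

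Simulation (6,000 runs per setting, r = 0.6) agrees for completers. With last value carried forward for 6 of 30, the within-arm rates are 29%, 47-48% and 64-65%. In the same simulations the between-arm ANCOVA (arm, baseline, age) rejects in 4.8-5.4% of trials among completers and 4.0-4.7% with last value carried forward.

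**2. Apparent effect size when the true between-arm effect is zero.** The SD of change equals √(2(1 − r)) baseline SDs, so the mean within-arm change is δ√(2(1 − r)).

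- r = 0.5: the multiplier is 1.00, giving 0.30 to 0.50 baseline SD.
- r = 0.7: the multiplier is √0.6 = 0.775, giving 0.23 to 0.39 baseline SD.

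These are completer figures. With 20% carried forward from baseline they shrink by a factor of 0.8, to 0.19-0.40 overall.

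**3. Precision of the between-arm alternative.** SE = √((1 − r²)(1/n₁ + 1/n₂)) in baseline SDs, with N − 4 degrees of freedom.

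| Arms | Detectable at 80% power, r = 0.5 | r = 0.7 |
|---|---|---|
| 24 v 12 | 0.89 | 0.73 |
| 24 v 16 | 0.81 | 0.66 |
| 30 v 15 | 0.79 | 0.65 |
| 30 v 20 | 0.72 | 0.59 |

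The within-arm SE is √(2(1 − r)/n₁). For 24 v 16 at r = 0.5 the 95% half-widths are 0.567 between arms and 0.422 within, a ratio of 1.34. For 30 v 15 at r = 0.7 they are 0.456 and 0.289, a ratio of 1.58. The other settings fall between.

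**The case against.** The best defence is that a between-arm analysis may already be covered. The list of compared outcomes is open-ended, the ANCOVA stands under the secondary-outcome heading, and Table 3 places these scales among the secondary assessments. The one-arm sentence could then be an addition. This is fair: a comparison is not excluded. But it is not specified, and a separate sentence limited to one arm points the other way.

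Second, the effect-size sentence may not be meant for these scales. C.1 ties the estimates for a future trial to weight, body composition, lipids and inflammatory markers. That reading is possible. However, the sentence in D.1.b directly follows the one on self-efficacy and social support and refers back to the exploratory analyses without exception.

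Third, the rejection rates above are power to detect a real within-arm shift, and become errors only if the change is attributed to the intervention. That is correct, and it is why they are offered as illustration. Attribution to the intervention is nonetheless what an effect size for a randomized trial requires.

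Two further limits stand. Regression to the mean is only a possibility, since eligibility (C.3.b) does not select on these scales. And with detectable differences of 0.59-0.89 SD, the between-arm result will be imprecise.

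**Conclusion.** The concern holds, as a minor one. For two constructs the intervention targets, the plan specifies an uncontrolled within-arm change and does not specify the randomized comparison that the data appear to allow. The bias, if the change is used as an effect size, equals the control-arm shift, which the documents do not let one estimate. Under an assumed shared shift of 0.3-0.5 SD of change it would be 0.23-0.50 baseline SD among completers, or 0.19-0.40 under the plan's carry-forward rule. The textual finding does not depend on those figures. It does rest on reading item 8 of C.7.b as covering both arms. The analysis is exploratory, neither Specific Aim lists these scales, and the primary feasibility outcome is unaffected.

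**What to change.** In D.1.b, replace the one-arm sentence with: *Changes in social support and self-efficacy will be compared between the weight-loss and active control groups with the same baseline- and age-adjusted ANCOVA as the other secondary outcomes, and reported as an estimate with a 95% confidence interval. Within-arm changes will be descriptive only.*

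In C.7.b item 8, state that participants in both groups complete the scales at baseline and at 15 weeks. If only one arm is to complete them, say so, and state that the within-arm change will not be used as an effect size for the larger trial.

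The cost is one replaced sentence and one clarification, with no new data if both arms already complete the scales. The price is the wider interval shown above, so the result should be read as an estimate with its uncertainty and not as a powered test.

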also a risk of muscle injury, which may require medical attention, may take several months to heal, and may limit activities of daily living for a period of days, weeks, or months. Participants will be informed that there is an increased risk with starting a physical activity program and be advised of all of the potential risks. Additionally, [name] and research staff with training in exercise physiology and behavioral changes will be directly involved in conducting physical fitness tests and delivering exercise components.

There is a slight risk of breach of confidentiality, but steps are in place to protect participants' personal information. Electronic data will be stored behind a firewall and accessed only by study staff through password-protected computers. Paper-based data will be stored in a locked cabinet within a locked file room.

Collectively, the participants will be assuming no more than minimal risk in completing the assessment protocol and the minimal risk inherent to completing the assessments will be mitigated via stringent pre-test medical screening and during testing supervision.

E.2 Benefits of participation

Participants may gain awareness of healthy eating and physical activity from evidence-based program. Participants in the telephone-based counseling group will receive a physical activity tracker (e.g., Fitbit) at the beginning of the study, and weekly telephone-based weight loss counselling for 15 weeks. Participants in the active control group will also receive a physical activity tracker and lifestyle modification manual at the end of the study. All participants will receive regular body weight, body composition, and blood tests for lipid profiles and inflammatory biomarkers free of charge.

E.3 Adverse events

Adverse events, including any unfavorable and unintended sign (e.g., abnormal laboratory finding or symptom) will be collected as they occur, regardless of whether it is considered related to the weight loss intervention. Musculoskeletal injuries and previously undocumented major medical events incurred during the intervention will be systematically collected on all participants during the study period using standardized forms from our prior work. Patients will have instructions to contact the PI or their primary health providers to discuss and manage any possible side effects. The PI, study coordinator should immediately be contacted in the event such a problem arises.

E.3.a Severity

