- 1) Serious adverse event: Any adverse event that is fatal or life threatening, is permanently disabling, requires inpatient hospitalization or prolongs hospitalization, or results in a congenital anomaly or birth defect;
- 2) Life-threatening event: Any adverse event in which the subject is at immediate risk of death from the reaction as it occurs; does not include a reaction that, if it occurs in a more serious form, might cause death;
- 3) Unexpected event: Any adverse event that is not identified in nature, severity, or frequency in the investigator brochure, study protocol, consent form, or IND application; or the event is more serious than anticipated.

E.3.b Association

- 1) Definitely Related: An adverse event that has a timely relationship to the administration of the study intervention and follows a known pattern of response for which no alternative cause is present;
- 2) Probably Related: An adverse event that has a timely relationship to the administration of the study intervention and follows a known pattern of response, but for which a potential alternative cause may be present;
- 3) Possibly Related: An adverse event that has a timely relationship to the administration of the study intervention, follows no known pattern of response, but a potential alternative cause does not exist;
- 4) Unrelated: An adverse event for which there is evidence that it is definitely related to a cause other than the study intervention; in general, no timely relationship to the administration of the drug/procedure exists, or if so, the event does not follow a pattern of response and an alternative cause is present.

E.3.c Documentation

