The adverse event form will be used by study staff to report injuries or other adverse events reported by participants throughout the study. The patient will be observed and monitored carefully until the condition resolves, stabilizes, or its cause is identified. All adverse events, including laboratory abnormalities, will be followed up according to good medical practices. Information to be recorded includes: 1) specific type of reaction; 2) duration of reaction; 3) severity/grade of reaction according to the NCI Common Terminology Criteria for Adverse Events v4.0 (CTCAE); 4) suspected cause of the reaction (i.e. possibly or probably related to one of the following: study treatment, progression of disease, concurrent medications, concurrent illness, or other factors); 5) changes made in the administration of the study intervention and other actions taken to alleviate the clinical event; and 6) patient's response to medical interventions.

E.3.d Reporting

In accordance with IRB guidelines, serious adverse events will be reported within 10 days of the investigator's or research staff members' learning of the event to OSU IRB. OSU IRB Event Reports should be submitted through BuckIRB at: <http://orpp.osu.edu/irb/buck-IRB/>. Events resulting in temporary or permanent interruption of study activities by the investigator or sponsor to avoid potential harm to subjects should be reported within 48 hours whenever possible.

All events that may represent unanticipated problems involving risks to subjects or others will be promptly reported (as described above), regardless of whether they occur during or after the study, or involve a subject who has withdrawn from or completed study participation. If changes to the research or consent process are proposed as a result of the event, or if additional information will be provided to current and/or past participants, a protocol amendment will be submitted for IRB review.

Related events involving risk but not meeting the prompt reporting requirements will be reported to the IRB in summary form at the time of continuing review.

E.4 Confidentiality

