Participants enrolled in the study will be assigned to a study ID. Individuals will not be identified by name or by any other personal identifying information in reports, or publications resulting from this study. All information will remain de-identified. Thus, risk of disclosure of confidential medical information will be essentially nonexistent. Additionally, all data will be number coded and stored in a password protected files and a locked research office that can only be accessed by the research staff. These procedures have been successfully used to protect confidentiality in our prior studies.

Study patients may voluntarily withdraw at any time from the protocol. The reasons for discontinuation of the study will be documented in the patient record and data collection forms. A letter to the PI in writing

F. Ethical and Regulatory Considerations

F.1 Institutional Review Board

Prior to initiating the research project and conducting any research project activities the PI will obtain written approval to conduct the research project from the appropriate institutional regulatory bodies. Should changes to the research project protocol become necessary, the PI will submit protocol amendments in writing to the IRB for approval prior to implementation.

F.2 Informed Consent

As noted in section 3.2.3, consent will be sought and obtained via phone and verbal consent process completed prior to initiating any research project procedures. Each element of the consent will be verbally explained to the potential participant. The woman will be given an opportunity to ask questions and have the questions answered to her satisfaction. Once the individual understands each element of the verbal consent, including the purpose, requirements, benefits, risks, confidentiality, right to withdraw, and contact person, then and only then will it will

be documented that the individual consented to participate in the study.

F.3 Compliance Monitoring

In accordance with IRB guidelines, the study program will be reviewed by the IRB every 12 months or less. Deviations from the protocol must be documented in the medical record and reported immediately to the PI. Deviations that meet the criteria for Immediate Event Reporting (<http://orrp.osu.edu/irb/event/index.cfm>) such as those that increase risks to subjects and/or compromise scientific integrity will be reported immediately to the IRB.

F.4 Data and Safety Monitoring Plan

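### E.3.a counts disability as serious only if it is permanent, so the months-long reversible injury foreseen in E.1 has no explicit prompt-reporting trigger in E.3.d, and F.4 points another way

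*Combined protocol and SAP*

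**What the plan says.** All references are to the combined protocol and SAP.

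- **E.3.a (Severity)** defines a serious adverse event through alternatives: "Any adverse event that is fatal or life threatening, is permanently disabling, requires inpatient hospitalization or prolongs hospitalization", or a congenital anomaly or birth defect. It defines an unexpected event as "Any adverse event that is not identified in nature, severity, or frequency in the investigator brochure, study protocol, consent form, or IND application". A further ground covers an event that turns out worse than was foreseen.
- **E.1 (Anticipated Risks)** names muscle injury from exercise, says that it may need medical attention, and adds that it "may take several months to heal, and may limit activities of daily living for a period of days, weeks, or months".
- **E.3.d (Reporting)** has three faster routes to the IRB. First, "serious adverse events will be reported within 10 days" of staff learning of them. Second, a 48-hour target applies to "Events resulting in temporary or permanent interruption of study activities by the investigator or sponsor to avoid potential harm to subjects". Third, "All events that may represent unanticipated problems involving risks to subjects or others will be promptly reported". Related events that involve risk but meet none of these go to the IRB in summary at continuing review.
- **F.3 (Compliance Monitoring)** has the study "reviewed by the IRB every 12 months or less".
- **F.4 (Data and Safety Monitoring Plan)** says that all adverse events follow IRB policy and the IRB's timeline, and that the IRB hears more often than usual if adverse events arise. It gives no number of days and no threshold. Table 5 has injury rates reviewed monthly within the study.

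**The concern.** The intervention is home-based aerobic and resistance exercise, guided by manual, telephone and optional video (C.4.c), in people who do not meet the activity guidelines at entry (C.3.b). Prolonged muscle injury is the most consequential exercise harm that E.1 names. It is also the kind of event that the seriousness definition misses, because lasting but reversible limitation has no criterion of its own.

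The criterion is also awkward to apply in time. The 10-day period runs from learning of the event. For an injury that heals over months, whether the disability is permanent will often be unknown on day 10.

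What is at stake is when someone outside the study team looks at such an injury. F.4 describes no independent monitoring board; adverse events are reviewed by the investigators and the team. The IRB is therefore the independent check, and its notification trigger should be clear for the injury that the protocol itself foresees.

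**Working it through.** The plan states no figure on this point, so the check is to take one case through the text. The case is a muscle injury treated without admission, limiting daily activities for some months, then fully resolving, and judged related to the intervention.

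**Step 1. Is it serious under E.3.a?**

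| Criterion | Met? |
|---|---|
| Fatal or life threatening | No |
| Permanent disability | No, it resolves |
| Inpatient or prolonged hospital stay | No, by construction |
| Congenital anomaly or birth defect | No |

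It is not serious. The same injury with an admission would be.

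**Step 2. Is it unexpected under E.3.a?**

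- Nature: identified in E.1, so no.
- Severity: identified in E.1 (months of limited activity), so no.
- More serious than anticipated: no, if it stays within E.1's description.
- Frequency: undetermined, because E.1 gives no rate.

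**Step 3. Which E.3.d route applies?**

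- 10 days: no, because it is not serious.
- 48 hours: only if study activities are interrupted to avoid harm.
- Unanticipated problem: a matter of judgement. E.3.d does not define the term, and Step 2 leaves only frequency open.
- Otherwise: the summary at continuing review. This route is for related events, so the result depends on the attribution made under E.3.b.

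**Step 4. What does F.4 add?** It promises feedback sooner than the regular review for any adverse event, without a deadline. For this case E.3.d says continuing review and F.4 says earlier, at no stated time.

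**Step 5. How long could the gap be under E.3.d alone?** The inputs are a review interval of at most 12 months (F.3), a 15-week intervention (C.4.a), accrual of 4-5 a month and a maximum of 50 participants (C.3.c).

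- Interval in intervention lengths: 52 weeks / 15 weeks = about 3.5.
- Accrual over the interval: 12 × 4 = 48 to 12 × 5 = 60, against a maximum of 50.

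At the longest permitted interval, with accrual on plan and the injury early in that interval, nearly all participants could be enrolled before the IRB saw the event. This is a ceiling. F.3 allows shorter intervals, and F.4, if followed, shortens the gap.

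**The case against.** The other side has substantial points, and several stronger readings that a reader might infer do not survive them.

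- **That an event must involve permanent disability to be serious.** This does not follow. Death, threat to life and hospitalization are separate criteria. The gap concerns the disability criterion alone.
- **That the injury can never be unexpected.** The frequency ground is open, and the routes for unanticipated problems and for interrupted activities are not limited to serious events.
- **That the IRB hears only at continuing review, and otherwise only the study team knows.** F.4 contradicts this. It refers all adverse events to IRB policy and promises more frequent feedback. That policy is not among the documents, so what it would require cannot be settled here.
- **That the permanence criterion is unusable.** E.3.c follows events until they resolve or stabilize, and nothing bars reclassifying one later. The criterion is hard to apply inside 10 days, not impossible to apply.
- **That serious-event counts taken into a larger trial would understate harm.** Nothing in the documents says that such counts are carried forward. The planned safety measure in D.1.a is intervention-related adverse events. E.3 collects musculoskeletal injuries on all participants, and E.3.c records duration and CTCAE grade, whatever the serious label.

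What remains is that F.4 does not close the gap. It has no deadline, and E.3.d is where the protocol sets out its IRB reporting times. Read together, the two sections give different answers for the same injury.

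**Conclusion.** The concern holds in a limited form. The only disability criterion in E.3.a is permanence, so E.1's prolonged but reversible injury, if not hospitalized, has no explicit prompt trigger in E.3.d unless it interrupts the study or may be an unanticipated problem. If related, its default is the continuing-review summary, and F.4 conflicts with that default.

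The delay is between 10 days, had the event counted as serious, and a ceiling of 12 months under E.3.d and F.3 alone. The ceiling assumes the longest permitted interval, an injury early in it, and no earlier feedback under F.4. The documents give no injury rate, so no expected number of affected participants can be stated.

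This is a weakness in safety oversight that should be corrected because the correction is cheap. It does not affect the completion-rate analysis or the efficacy comparisons, and the injuries would still be recorded and graded.

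**What to change.** 1. In E.3.a, replace the permanent-disability criterion with: *results in persistent or significant disability*.
2. Apply it identically in both arms. Do not tie persistence to the participant's next study contact. Weekly calls exist only in the intervention arm (C.4.a, C.4.d), while for controls the plan describes materials at the start and end (C.5) and assessments at baseline and 15 weeks (C.7). A contact-based trigger would classify the same injury differently by arm.
3. Reconcile E.3.a, E.3.d and F.4 into one stated IRB reporting timeline for prolonged, non-hospitalized injuries, with a number of days in place of F.4's open promise.

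Optional and editorial: retitle E.3.a, since it defines seriousness and expectedness while E.3.c already assigns severity to the CTCAE grade.

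The cost is a wording amendment submitted to the IRB and possibly a few more 10-day reports among up to 50 participants.
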